1.0 Introduction

The coflex® Interlaminar Technology - manufactured by Paradigm Spine - is intended for use as a permanent implant between the lamina of 1 or 2 lumbar motion segments in the treatment of moderate to severe lumbar spinal stenosis. The device is specifically designed to provide stabilization without fusion in cases of stenosis with or without facet joint hypertrophy, subarticular recess stenosis or foraminal stenosis. It is restricted for use to one or two levels in the region of L1 – L5.

The height of the neuroforamen is maintained and the facet joints will be relieved. By this a further destruction is prevented. Unlike conventional stabilization methods as for example spinal fusion, the function of the segment will be maintained and adjacent structures will be effectively protected.

Possible risks, which could occur after implantation of the coflex® Interlaminar Technology are breakage of the implant, displacement of the implant, pain which is caused by the implant, infections, bleedings and hematoma. The benefit of the study lies in the fact that first-time retrospective data is raised for potential improvement regarding therapy of lumbar back pain with the treatment of the lumbar spinal stenosis, which, in the future, can lead to an improvement of the therapy.

In this study, Paradigm Spine will retrospectively collect clinical and radiographic data for patients treated with the coflex® Interlaminar Technology during normal conditions of use. This data will provide evidence to support publications and marketing.

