2.2 Secondary Objectives

The secondary objectives of this study are:

- To measure and compare patient reported outcomes (e.g., VAS, Patient Satisfaction and ODI) at baseline and final follow-up
- To measure and compare clinical and radiologic outcomes at baseline and final follow-up
- To measure and compare the clinical, radiologic, and patient reported outcomes at interim follow-up visits
- To assess the impact of demographics and risk factors on clinical, radiologic, and patient reported outcomes

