4.0 Study Design

This is a retrospective, multi-center, post-market study collecting clinical, radiographic, and patient reported outcomes for subjects who have been treated 1 or 2 levels with the coflex® Interlaminar Technology or decompression with or without fusion.

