4.1 Endpoints

Patient reported outcomes will be assessed as part of the primary objective.

Clinical and radiologic outcomes, demographics and risk factors will be assessed as part of the secondary objectives. These include, but are not limited to:

- Age
- Gender
- Ethnicity
- Height and Weight
- BMI
- Narcotics use
- Comorbidities
- Bone Density
- Presenting Symptoms
- Radiologic Data (Anterior/Posterior and Flexion/Extension films, as well as, MRI and/or CT Scan used to confirm diagnosis of spinal stenosis)
- Operative Data
- Intra-Operative Complications
- Return to Work
- Changes in Activities of Daily Living (ADL)
- Patient Satisfaction
- Repeat Surgery Details

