5.0 Statistical Analysis

5.1 General Information

All continuous outcome measurements at follow-up time points will be compared to baseline values using a t-test for superiority. Categorical outcome measurements will be compared using a Fisher's exact test for superiority. Statistical significance for these analyses will be demonstrated with a p-value less than 0.05.

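### The blanket superiority-over-baseline test cannot show that a radiologic measure is maintained, and no favourable direction is set by procedure

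*Combined protocol and SAP*

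**What the plan says.** Section 5.1 gives one rule for continuous data: "All continuous outcome measurements at follow-up time points will be compared to baseline values using a t-test for superiority". The threshold follows: "Statistical significance for these analyses will be demonstrated with a p-value less than 0.05". Whether the test is one- or two-sided is not stated, and no margin is given.

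Radiologic data fall under this rule through section 2.2, which lists as a secondary objective "To measure and compare clinical and radiologic outcomes at baseline and final follow-up". Section 4.1 describes the material by imaging type only: "Radiologic Data (Anterior/Posterior and Flexion/Extension films, as well as, MRI and/or CT Scan used to confirm diagnosis of spinal stenosis". Neither foraminal height, nor motion in degrees, nor an adjacent-level measure is named as a variable. Section 5.3 gives no separate radiologic analysis.

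The expected radiographic effect appears only in section 1.0: "The height of the neuroforamen is maintained and the facet joints will be relieved", and, in a sentence that contrasts the device with fusion, "the function of the segment will be maintained and adjacent structures will be effectively protected".

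Under section 4.0 the population is patients "treated 1 or 2 levels with the coflex® Interlaminar Technology or decompression with or without fusion". Fused and non-fused patients are therefore in the same study, and section 5.1 does not distinguish them.

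**The concern.** Superiority over baseline suits pain and disability, where patients are expected to improve. It does not suit a measure for which the good result is no meaningful loss. If motion or foraminal height is analysed as a continuous outcome, the rule in section 5.1 asks whether it has become better than before surgery. The background text says it stays the same.

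Two misreadings then become possible. A device that keeps the measure unchanged will usually give a non-significant result, which could be reported as no benefit. Or the non-significant result could be reported as maintenance, which is easiest to obtain when few images are available. The title announces radiographic performance, and section 1.0 says the data are meant to support publications and marketing, so a maintenance statement resting on the second misreading is a practical risk.

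The fused patients add a further difficulty. Section 1.0 itself sets fusion apart from maintained function, so treated-level motion does not have the same favourable direction in every procedure group. The plan assigns none.

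**Working it through.** The plan has no radiologic effect size, SD, margin or power statement, so there is no figure to reproduce. What follows is illustrative.

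**Inputs**
- From section 5.1: t-test against baseline, significance at p < 0.05. Sidedness is not stated, so both readings are shown.
- Assumed: a paired test on within-patient change, with standardised true change d = mean change / SD of change (negative d is a loss). The numbers of paired images are also assumed, because the documents do not give them. The upper end, 5000, is the collection target in the Protocol Summary.

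**1. Measure perfectly maintained (d = 0).** The chance of a significant improvement equals the test's false-positive rate: 0.05 one-sided, or 0.05 / 2 = 0.025 in the favourable direction two-sided. This holds at every n from 30 to 5000. More images do not help.

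**2. Real loss, non-significant result.** The test statistic follows a noncentral t distribution with n − 1 degrees of freedom and noncentrality d√n. For d = −0.5 and n = 30 the noncentrality is −0.5 × √30 = −2.74, against two-sided critical values of ±2.05.

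| Paired images | Two-sided test non-significant, true loss 0.5 SD |
|---|---|
| 30 | 24.6% |
| 50 | 6.6% |
| 100 | 0.1% |

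If the test is one-sided for improvement, a loss is almost never flagged. At n = 30 and d = −0.5 the probability of significance is 0.00001, so the result is non-significant practically always.

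**3. Trivial loss, large sample.** With d = −0.1, a two-sided test declares a significant loss with probability 0.290 at n = 200, 0.885 at n = 1000 and about 1.00 at n = 5000. Significance here says little about whether the loss matters.

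**4. A test that asks the right question.** Let m be the largest acceptable mean loss in SD units. Maintenance is concluded if the two-sided 95% CI for mean change lies wholly above −m. By normal approximation, with no true change and 80% power, n = ((1.960 + 0.842) / m)².

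| Assumed margin m (SD) | Calculation | Paired patients needed |
|---|---|---|
| 0.1 | 7.849 / 0.01 | 785 |
| 0.2 | 7.849 / 0.04 | 197 |
| 0.3 | 7.849 / 0.09 | 88 |
| 0.5 | 7.849 / 0.25 | 32 |

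At m = 0.2 the power is 0.52 with 100 pairs, 0.81 with 200 and 0.99 with 500. Unlike the superiority test in step 1, this one gains from more data when the measure is maintained. If there is a true loss, m is replaced by m minus that loss: a margin of 0.2 with a true loss of 0.1 needs 785 pairs.

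**The case against.** The strongest reply is that the plan never sets out to prove maintenance. The relevant sentences are introductory, section 2.2 promises only to measure and compare, and section 4.1 names films rather than measurements. On this view the test is faulted for failing to support a claim that the study does not make, and the more basic gap is that no radiologic endpoint is defined. Much of this stands. The point is conditional: it applies to whatever continuous radiologic measure is analysed. It is not removed, because section 5.1 exempts nothing, no other section supplies a different radiologic analysis, and the only radiographic benefit described is one that this test cannot show.

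A reader might also infer more than the documents support:
- *That the test points the wrong way for fused segments.* No favourable direction is given for any radiologic variable or group, so the direction is undefined rather than shown to be wrong. The argument concerns treated-level motion and does not carry over to foraminal height.
- *That the study fails if the device works as described.* There is no radiographic success criterion. The primary endpoint in section 5.2 is follow-up duration and secondary surgery.
- *That few films guarantee an apparent finding of no change.* Under a two-sided test they make it more likely, not certain: 24.6% at 30 pairs in the example above.

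**Conclusion.** The concern holds in a limited form. The superiority rule in section 5.1 covers any continuous radiologic measure compared with baseline, and neither a significant nor a non-significant result from it can establish that the measure is maintained. Under no change it succeeds 5% of the time one-sided, or 2.5% in the favourable direction two-sided. With a 0.5 SD loss and 30 pairs, a two-sided test misses the loss about a quarter of the time. Because fused patients are included and no direction is set by procedure, a single superiority comparison of treated-level motion is not interpretable across groups.

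The false-positive rates follow from the test itself. The other figures depend on assumed losses, margins and numbers of paired images. The point should be addressed, but it is moderate in weight because it touches a secondary objective only. Superiority over baseline remains a reasonable question for VAS and ODI.

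**What to change.** In section 5.1:
- Limit superiority over baseline to outcomes where improvement is expected, such as VAS and ODI.
- Name each continuous radiologic measure that will be analysed. Report its mean change from baseline with a 95% CI, separately by procedure, with the number of paired images.
- Show treated-level motion in fused segments apart from the other groups, and do not score it in the same direction.
- Allow a conclusion of maintenance only if the CI excludes a loss larger than a margin that is justified and fixed before the data are seen. The margin must be for the group mean. Film measurement error alone does not justify it, since it describes single readings and not how large an average loss is acceptable.

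The cost is SAP wording and the work of justifying a margin; no extra data collection is needed. The downside is that with few paired images the maintenance conclusion may not be reached. With an assumed 0.2 SD margin and no true change, about 197 paired patients per measure and procedure group give 80% power. That is small against the target of about 5000 patients, but the plan does not say how many have images at both times.

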Study Design	Retrospective, multi-center, post-market clinical study
Devices	coflex® Interlaminar Technology
Data Collection	Clinical, radiologic and patient reported outcomes data will be collected for approximately 5000 patients from 50 sites
Study Duration	Up to 6 months for data collection Start Date: June 2013 End Date: April 2017
Study Objectives	
Primary Objective:
 
• To assess the operative details and safety outcomes associated with the use of the coflex device• To assess post-operative adverse events• To assess post-operative follow-up duration 
Secondary Objectives:
 
• To measure and compare patient reported outcomes (e.g., VAS, Patient Satisfaction and ODI) at baseline and final follow-up• To measure and compare clinical and radiologic outcomes at baseline and final follow-up• To measure and compare the clinical, radiologic, and patient reported outcomes at interim follow-up visits• To assess the impact of demographics and risk factors on clinical, radiologic, and patient reported outcomes•
Inclusion Criteria	Patients must meet the criteria specified in the device labeling including radiographic confirmation of at least moderate lumbar stenosis, which narrows the central spinal canal at one or two contiguous levels from L1-L5 that require surgical decompression.
Exclusion Criteria	There are no exclusion criteria's for this study.

Risk/Benefit Assessment

The study is a retrospective analysis of medical records that poses no risk to the patients and minimal risk to loss of patient privacy. All results will be de-identified in the process of data review. There are no benefits to the subject as this data is being collected to obtain additional clinical evidence to support publications and marketing.

Study Abbreviations

Abbreviation	Definition
BMI	Body Mass Index
FDA	Food and Drug Administration
GCP	Good Clinical Practice
HIPAA	Health Insurance Portability and Accountability Act of 1996
ICH	International Committee on Harmonization
IRB	Institutional Review Board
MRI	Magnetic Resonance Imaging
CT	Computed Tomography
DEXA	Dual Energy X-ray Absorptiometry

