4.2 Data Collection Summary

Subjects will have undergone a decompression surgery with the coflex® Interlaminar Technology, 1 or 2 level decompression with or without fusion according to the physician's standard procedures. Table 1 describes the anticipated time points which will be collected as part of the retrospective data review. Please see Section 4.4, Data Collection Procedures for additional details regarding the data points intended to be captured at the designated time points.

	Baseline	Surgical Treatment	Post-Operative Hospital Stay	Follow-Up Visit(s)
Demographics & Risk Factors	X			
Prior Surgery Detail (If available)	X			
Diagnosis	X			
Operative Summary		X		
Procedure Payer Information		X		
Secondary Treatments			X	X
Complications		X	X	X
Work Status / ADL (If available)	X		X	X
Patient Questionnaires (If available)	X	X	X	X
Diagnostic Imaging History	X	X	X	X

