4.4.1 Baseline Visit

- Diagnosis
 - Presenting symptoms
 - Documented failed conservative treatment
 - Patient reported outcome questionnaires, if available
 - Prior treatment details
- Pre-Operative Demographics
 - Date of visit
 - Age
 - Gender
 - Race
 - Ethnicity
 - Work Status / ADL
 - Height (in)
 - Weight (lbs)
 - BMI

- Risk Factors
 - Tobacco Use
 - Alcohol Use
 - Comorbidities
 - Diabetes
 - Bone Density
 - Medications
- Diagnostic Imaging
 - MRI and CT of affected lumbar levels
 - Radiographs

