4.4.4 Follow-Up Visits

The following longitudinal data will be collected for all follow-up clinic visits through final follow-up:

- Work status / ADL
- Compliance with postoperative protocol/restrictions (if applicable)
- VAS (as available)
- ODI (as available)
- Patient satisfaction (as available)
- Complications
- Secondary treatments
- Narcotics use
- Diagnostic Imaging
- Incidence of Epidural Steroid Injections (ESI)

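### Section 5.1 names Fisher's exact test, with no comparator, as the only categorical method; used for baseline versus follow-up in the same patients, it treats paired values as independent

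*Combined protocol and SAP*

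**What the plan says.** Section 5.1 has one sentence for each type of outcome. For continuous outcomes: "All continuous outcome measurements at follow-up time points will be compared to baseline values using a t-test for superiority". For categorical outcomes: "Categorical outcome measurements will be compared using a Fisher's exact test for superiority". The first names baseline as comparator but does not say that the t-test is paired. The second names no comparator. Both are judged at p below 0.05, with sidedness not stated. Sections 5.2 and 5.3 add no other categorical test.

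Other sections call for within-patient comparison. A secondary objective in 2.2 is "To measure and compare clinical and radiologic outcomes at baseline and final follow-up". Section 4.1 lists "Changes in Activities of Daily Living (ADL") among the items assessed under the secondary objectives. Section 4.4.1 records "Work Status / ADL" before surgery. Section 4.4.4 lists it again, under the statement "The following longitudinal data will be collected for all follow-up clinic visits through final follow-up". The table in 4.2 marks it at baseline, hospital stay and follow-up, where available. No ADL instrument or scale is named.

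**The concern.** Fisher's exact test assumes two independent samples. A patient's work status before surgery and at follow-up are two values from one person and will usually be correlated. A 2×2 table of time point by status ignores that correlation, so the test uses the wrong variance for the change.

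An analyst following 5.1 has one categorical test and, in the same paragraph, one named comparator, which is baseline. Applying Fisher's test to baseline versus follow-up is therefore a natural way to carry out the plan for ADL change. At stake is whether a real change in a secondary outcome is detected, and whether the reported p-value means what 5.1 says it means.

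**Working it through.** The plan gives no power, rate or correlation for these items, so there is no figure of its own to reproduce. The inputs below are assumptions, except the 0.05 level (5.1), which is taken as two-sided.

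**1. Large-sample size of an unpaired test on paired data.** With equal proportions p at both times and within-patient correlation ρ, the difference between two proportions from n pairs has variance 2p(1−p)(1−ρ)/n. An unpaired test uses 2p(1−p)/n. Its true two-sided size is therefore 2[1 − Φ(1.96/√(1−ρ))]:
- ρ = 0: 5.0%
- ρ = 0.3: 1.96/√0.7 = 2.343, giving 1.9%
- ρ = 0.5: 1.96/√0.5 = 2.772, giving 0.6%
- ρ = −0.3: 1.96/√1.3 = 1.719, giving 8.6%

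**2. Complete pairs, binary item.** The joint probability of a positive value at both times is p₁₁ = p₁p₂ + ρ√[p₁(1−p₁)p₂(1−p₂)]. For 40% to 33% and ρ = 0.3, p₁₁ = 0.132 + 0.3 × 0.2304 = 0.2011. The discordant probabilities are 0.40 − 0.2011 = 0.1989 and 0.33 − 0.2011 = 0.1289. Fisher's test was applied to the two margins and exact McNemar to the discordant pairs. Results are by exact enumeration for 100 and 300 pairs and by simulation (20,000 runs) for 1000.

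| Pairs | ρ | Type I error (40%/40%), Fisher vs McNemar | Power (40% to 33%), Fisher vs McNemar |
|---|---|---|---|
| 100 | 0.3 | 1.2% vs 3.2% | 9.8% vs 17.7% |
| 100 | 0.5 | 0.3% vs 3.0% | 6.4% vs 23.1% |
| 300 | 0 | 4.1% vs 4.1% | 39.6% vs 39.7% |
| 300 | 0.3 | 1.5% vs 4.0% | 37.6% vs 52.7% |
| 300 | 0.5 | 0.4% vs 3.8% | 35.4% vs 67.3% |
| 1000 | 0.3 | 1.9% vs 4.7% | 93.3% vs 97.0% |
| 1000 | 0.5 | 0.4% vs 4.2% | 96.1% vs 99.5% |

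At 5000 pairs (3000 runs) Fisher's type I error is still 1.8% and 0.3%, but both tests have full power.

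**3. Negative correlation.** At ρ = −0.3 and 50% at both times, Fisher's type I error is 7.5% (100 pairs) and 7.9% (500 pairs), so the direction reverses.

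**4. Partly paired data.** If some patients have only a baseline value, Fisher's test can use them and McNemar's cannot. Power for 40% to 33%, with follow-up missing at random (10,000 runs), Fisher vs exact McNemar:

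| Baseline / follow-up | ρ = 0.3 | ρ = 0.5 |
|---|---|---|
| 300 / 180 | 30% vs 33% | 28% vs 44% |
| 500 / 300 | 49% vs 51% | 50% vs 67% |
| 1000 / 300 | 59% vs 53% | 60% vs 68% |
| 1000 / 200 | 45% vs 36% | 46% vs 49% |

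**5. A single table.** Take 100 patients, 50 working at baseline and 60 at follow-up, with 15 gains and 5 losses. Fisher's test on 50/100 versus 60/100 gives p = 0.20. Exact McNemar on 15 versus 5 gives p = 0.041. The choice of test alone moves the result across 0.05.

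**The case against.** - **The Fisher sentence may be meant for treatment groups.** The title and section 4.0 set coflex beside decompression with or without fusion, and only the continuous sentence mentions baseline. This reading is open, and under it the samples are independent and the pairing fault does not arise. But 5.1 would then have no method for categorical change from baseline, so the text needs an edit either way.
- **No test of ADL change may ever be run.** Section 5.3 says clinical outcomes will be summarized. Against that, 2.2 plans a comparison and 5.1 sets a significance threshold for outcome measurements generally. The documents do not settle it.
- **The power loss is largest for complete pairs and a small effect.** This stands. Work status/ADL is collected only where available, and step 4 shows the gap narrowing and, at a correlation of 0.3, reversing when baseline-only patients are numerous. For 40% to 25% with 300 complete pairs, both tests have about 99% power or more. At 100 pairs a gap remains: 56% vs 70% and 58% vs 86% at correlations of 0.3 and 0.5.
- **The study is large.** The plan is for "approximately 5000 patients from 50 sites". If nearly all had both values, the power loss would vanish. The availability condition makes that uncertain, and the size of the test would still be wrong.

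**Conclusion.** The concern holds in conditional form. Section 5.1 supplies one categorical test and no comparator. Where that test is used for baseline versus follow-up in the same patients, it is the wrong test for the design and does not deliver the 0.05 level. This rests on three conditions: the baseline reading is the one applied, work status/ADL is recorded in categories, and the two values are correlated. With positive correlation and 300 complete pairs, a change from 40% to 33% is detected with about 38% or 35% power instead of 53% or 67% (correlations 0.3 and 0.5). The numbers of pairs, rates and correlations are all assumed.

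Three stronger readings are tempting and are not supported:
- *That the plan definitely misapplies Fisher's test.* The text is ambiguous, and the test is not wrong in this way for independent groups or for post-operative-only items such as complications.
- *That the test is always conservative and always loses power.* Its direction depends on the sign of a correlation the documents do not give. Against a complete-pair McNemar test, its power also depends on how many patients have both values.
- *That the main conclusions are affected.* Follow-up duration and secondary surgical interventions (5.2) have no baseline value, so pairing does not touch them.

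The point is worth correcting because the better method is specific and cheap, but its reach is limited to secondary items.

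**What to change.** Amend 5.1 as follows:
1. Name the comparator for each test: baseline, another treatment group, or both.
2. For categorical change from baseline, replace Fisher's test with McNemar's test for binary items, or Bowker's test for more than two categories. Where several visits or many one-sided records are expected, use a GEE or mixed logistic model that also uses patients with only one value, and state its missing-data assumption.
3. State that the t-test against baseline is paired.
4. Report the number of patients with both values for each such comparison.
5. Keep Fisher's test for independent-group tables.

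The cost is a few sentences and standard software, with no new data. The downside is that McNemar's test uses only patients with both values. With many baseline-only records it can have less power than an unpaired test, which is the reason to allow the model-based option in item 2.

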Retrospective Evaluation of the Clinical and Radiographic Performance of coflex® Interlaminar Technology Versus Decompression With or Without Fusion.

Study ID Number: CRDC2016

Version 5.0

02November2016

Study Phase: Post-Market

Paradigm Spine

[name]

[name]

Change History

Version	Version Date	Summary of Changes
1.0	14June2016	Original
2.0	28June2016	Data collection to include 1 or 2 level decompression with or without fusion.
3.0	11July2016	Protocol title to reflect evaluation of coflex versus efficacy.
4.0	19August2016	Study Start Date and End Date applicable for Baptist IRB
5.0	22Novmeber2016	Data collection to include 5000 patients from 50 sites. Primary and Secondary Endpoints.

Table of Contents

Retrospective Evaluation of the Clinical and Radiographic Performance of coflex® Interlaminar Technology Versus Decompression With or Without Fusion.....	1
Table of Contents.....	2
Investigator Signature Page.....	3
Protocol Summary	4
Retrospective Evaluation of the Clinical and Radiographic Performance of coflex® Interlaminar Technology Versus Decompression With or Without Fusion.....	4
Study Abbreviations	5
1.0 Introduction	6
2.0 Study Purpose.....	6
2.1 Primary Objective	6
2.2 Secondary Objectives	6
3.0 Eligibility Criteria.....	7
3.1 Inclusion criteria.....	7
3.2 Exclusion criteria	7
4.0 Study Design	7
4.1 Endpoints	7
4.2 Data Collection Summary	8
4.3 Informed Consent	9
4.4 Data Collection Procedures	9
4.4.1 Baseline Visit	9
4.4.2 Surgical Treatment Visit.....	10
4.4.3 Post-Operative Hospital Stay	11
4.4.4 Follow-Up Visits	11
5.0 Statistical Analysis.....	11
5.1 General Information	11
5.2 Primary Endpoint	12
5.3 Secondary Endpoints.....	12
6.0 Study Management	12
6.1 Ethics.....	12
6.2 Data Entry	12

Investigator Signature Page

My signature below attests that I have read the contents of this protocol and agree to conduct the study according to the protocol and that the study will not be initiated without the approval of the appropriate Institutional Review Board or Independent Ethics Committee.

Investigator:

Print Name:

Signature:

Date:

Protocol Summary

Study Title	Retrospective Evaluation of the Clinical and Radiographic Performance of coflex® Interlaminar Technology Versus Decompression With or Without Fusion.
Purpose	To evaluate clinical, radiologic and patient-reported outcomes who have been treated 1 or 2 levels with the coflex® Interlaminar Technology or decompression with or without fusion.

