3.2 Exclusion criteria

There are no exclusion criteria for this study.

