5.3 Secondary Endpoints

The clinical outcomes will be summarized; however, since the collection of these measures is not standard of care, this data will only be collected as available. In addition, data will be used to analyze the association between coflex® Interlaminar Technology use and outcomes with age, ethnicity, race, workers' compensation, smoking status, and gender. New and/or worsening complications will be summarized.

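### No adjusted comparison of the procedures is prespecified, so differences in patient mix can be read as effects of coflex or of its comparators

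*Combined protocol and SAP*

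**What the plan says.** The title announces a comparison: "Interlaminar Technology Versus Decompression With or Without Fusion". Section 4.0 gives the design: "This is a retrospective, multi-center, post-market study collecting clinical, radiographic, and patient reported outcomes". Section 4.2 describes the non-coflex surgery as "1 or 2 level decompression with or without fusion according to the physician's standard procedures". No randomisation or other assignment rule appears. On eligibility, section 3.2 states: "There are no exclusion criteria for this study". Section 3.1 has one inclusion criterion, which refers to the device labelling.

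Section 5.1 names the only tests. For continuous outcomes: "All continuous outcome measurements at follow-up time points will be compared to baseline values using a t-test for superiority". For categorical outcomes: "Categorical outcome measurements will be compared using a Fisher's exact test for superiority". The threshold is: "Statistical significance for these analyses will be demonstrated with a p-value less than 0.05". Section 5.2 will use duration of follow-up care and secondary surgical interventions to judge the effectiveness of coflex, and names no method. Section 5.3 adds that "data will be used to analyze the association between coflex® Interlaminar Technology use and outcomes with age, ethnicity, race", then lists workers' compensation, smoking status and gender. It names no model either.

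**The concern.** When the choice of operation follows usual practice, the patients who receive each operation may differ in ways that also affect re-operation, pain and function. The inclusion criterion leaves room for this: it admits stenosis of moderate grade or worse, at one or two levels. A crude comparison then mixes the effect of the procedure with the effect of who was selected for it.

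The protocol says that the data will support publications and marketing. The conclusion at risk is therefore the one in the title, how coflex performs against the alternatives. The bias could favour either side, and a large sample does not shrink it. A larger sample only narrows the interval around the biased difference.

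**Working it through.** **What the text provides.** Three elements set side by side:

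- Comparison intended: coflex against decompression with or without fusion (title; both kinds of patient are collected under 4.0 and 4.2).
- Tests named: a t-test over time and a Fisher's exact test with its groups unstated (5.1). Neither takes covariates.
- Use of covariates: six factors in 5.3, with no model. The list omits treated levels, prior surgery, bone density, comorbidities and baseline VAS/ODI. The matching objective in 2.2 concerns the impact of risk factors on outcomes, not the comparability of procedure groups.

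No propensity score, matching, stratification, regression adjustment or site term appears anywhere in the document. Yet most of the material for adjustment is collected: age, gender, BMI, tobacco, diabetes, comorbidities and bone density (4.4.1), prior surgery where available and payer (table in 4.2), and treated levels (4.4.2).

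**Size, as an illustration.** The plan gives no effect size, event rate, power or split by procedure, so its figure of about 5000 cannot be reproduced. Everything below except 5000 and 0.05 is assumed:

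- no true effect of procedure;
- three equal procedure groups, 5000/3 ≈ 1,667 each, with two of them compared;
- one binary risk feature, with re-operation risk 8% without it and 16% with it;
- a two-sided test (the plan does not state sidedness).

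Crude incidence in a group where a fraction f has the feature: p = 0.08(1 − f) + 0.16f.

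- f = 0.50: 0.040 + 0.080 = 0.120
- f = 0.40: 0.048 + 0.064 = 0.112
- f = 0.35: 0.052 + 0.056 = 0.108
- f = 0.25: 0.060 + 0.040 = 0.100
- f = 0.20: 0.064 + 0.032 = 0.096

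For 50% v 20% the false difference is 0.120 − 0.096 = 0.024 (risk ratio 0.120/0.096 = 1.25). Its standard error is √[(0.120×0.880 + 0.096×0.904)/1,667] = 0.0107, so z = 2.23.

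Probability that Fisher's test gives p<0.05, by exact enumeration:

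- 50% v 20%: 58.7%
- 40% v 20%: 30.7%
- 35% v 25%: 10.6%
- 20% v 20% (balanced): 4.3%

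A Cochran-Mantel-Haenszel test stratified on the feature, in 20,000 simulated studies per scenario, rejects in 4.9%, 5.1% and 4.8% for the three unbalanced cases.

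**Sensitivity to the split and the risks.** A separate simulation split all 5000 patients into two groups, used risks of 5% v 10% or 8% v 16%, and set the feature at 30% v 40%, 30% v 50% or 20% v 50%. Fisher's test rejected in 9% to 77% of studies with a 1:1 split and in 9% to 59% with a 4:1 split. The stratified test stayed between 3.8% and 6.0%.

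**Effect of sample size.** The 0.024 does not depend on n. With 2,500 per group the standard error falls to √(0.192384/2,500) = 0.0088 and z rises to 2.74.

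**The case against.** The strongest reply is that 5.1 does not specify a between-procedure test. The t-test is a contrast over time, Fisher's groups are unstated, and the primary objective and section 5.2 speak of coflex alone. A reader might infer that the sponsor plans an unadjusted t-test between procedures. The text does not say so, and that reading should be dropped. The reply does not remove the point, though: either the comparison in the title has no specified analysis, or it falls to the only tests named, which are unadjusted.

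Other parts of the reply also stand. Covariates are not ignored: 2.2 and 5.3 plan to look at risk factors, and because 5.3 names no model, its analysis is unspecified rather than shown to be unadjusted. The absence of exclusion criteria does not mean an unrestricted mix, since 3.1 requires every patient to meet the labelling criteria. How far that narrows the groups cannot be judged from these documents. That stenosis grade and instability drive the choice of fusion is plausible but not stated. They are not listed as separate data points, although diagnosis and imaging are reviewed.

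**Conclusion.** The point holds in this form: treatment was not randomised, a comparison of procedures is the declared subject, and no adjusted analysis of that comparison is prespecified. Applying 5.1 as written to a procedure contrast can present patient mix as a procedure effect, and the nominal 0.05 is then not the real error rate.

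Two stronger statements are not supported. The documents do not show that such differences will be reported as effects, since the actual imbalance is unknown. Nor is 59% an estimate for this study. It is the largest of the three 1,667-per-group scenarios, all built on assumed risks, prevalences and group sizes. What the calculation shows is the mechanism: modest imbalance in one prognostic factor is enough to inflate false positives at this sample size, and stratifying on that factor, if it is recorded, restores roughly 5%.

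**What to change.** In 5.1 to 5.3, state the between-procedure contrasts, keeping decompression alone and fusion separate. Base each on a prespecified adjusted analysis; propensity-score weighting or regression would each serve.

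- **Covariates:** age, gender, BMI, tobacco, diabetes, comorbidities, bone density, prior surgery, treated levels, payer, and baseline VAS/ODI where available, plus site.
- **Imaging:** where the diagnosis or imaging records already under review give stenosis grade and spondylolisthesis or instability, record these and include them.
- **Reporting:** a balance table, a stated method for missing covariates (prior surgery and questionnaires are collected only if available), and adjusted differences with 95% confidence intervals.
- **Wording:** keep unadjusted Fisher's tests as descriptive only, and phrase conclusions as adjusted associations.

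The cost is a smaller effective sample, wider intervals, analysis time and some abstraction work across about 5000 charts. Sites that performed only one procedure will add little to a site-adjusted comparison. Confounding by factors not recorded will remain and should be acknowledged.
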